5 STUDY POPULATION

Older adult (≥65 years) patients attending to the primary care consultation in Portugal.

Exclusion criteria: Being acutely unwell in the last three weeks, and refuse to participate.

6 STUDY INTERVENTION

In the intervention group we will give enablement tools and talks with their GPs about how to issue the problem of polypharmacy.

7 STUDY ASSESSMENTS AND PROCEDURES

7.1 EFFICACY ASSESSMENTS

List and description of the procedures/evaluations to be used:

- Portuguese Beliefs about Medicines Questionnaire
 - For evaluation of the perception of medication
- EuroQol Five Dimensions Questionnaire
 - For assessment of the quality of life
- Two open-questions (one to assess the facilitators and the other to assess the barriers)
 - For assessment of the willingness to be deprescribed

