1 PROTOCOL SUMMARY

1.1 SYNOPSIS

Title:	Deprescribing: a portrait and out-comes of the reduction of Polypharmacy in Portugal (DePil17-20)
Study Description:	This study protocol comprises three phases. The first two phases will be nationwide and aim to evaluate the prevalence and patterns of polypharmacy and assess the barriers and facilitators of deprescribing perceived by older adults, as well as their willingness to be deprescribed and to self-medicate. The third and last phase will be a non-pharmacological randomised clinical study to measure the impact of enablement of older adults in their willingness to be deprescribed and related quality of life.
Objectives:	Primary Objective: Willingness to be deprescribed after the intervention Secondary Objectives: Quality of life after the intervention
Study Population:	Older adults (≥ 65 years) in Portugal
Description of Study	In the intervention group the investigators will give enablement tools and talks with their General Practitioners about how to issue the problem of polypharmacy.
Intervention:	
Study Duration:	36 months.
Participant Duration:	6 month.

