3 OBJECTIVES AND ENDPOINTS

Primary objective is to assess the enablement of older adults while being Deprescribed in the rise of Willingness to be Deprescribed.

Secondary objective is to assess the enablement of older adults while being Deprescribed in the rise of their Quality of Life outcome.

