4 STUDY DESIGN

This is a three-phase study:

1. Cross-sectional, analytical study of the prevalence and patterns of polypharmacy, namely sociodemographic and clinical profiles (age, genre, area of residence and years of study) and about medication (number of drugs and their active component), in older adults attending Primary Care in Portugal.
2. Cross-sectional, triangulation study of older adults' perception of Barriers to and Facilitators of Deprescribing, Willingness to be Deprescribed and Willingness to Self-medicate.
3. Non-pharmacological randomised clinical study of the impact of enablement of older adults in their willingness to be Deprescribed and related Quality of Life.

Phase I: prevalence of polypharmacy in older adults attending primary care in Portugal

Design

Cross-sectional, analytical study.

Setting

Primary Care Centres in Portugal will be randomly selected from the five main-land Portuguese Healthcare Administrative Regions and two Autonomous Regions (Madeira and Azores), in order to obtain a national geographical representative sample.

Sample size

Since the prevalence of polypharmacy in older adults is unknown, we used as base of population all older adults in Portugal. For the study, we used a 95% confidence interval (CI) and a maximum precision error of 5%, so a minimum of 385 patients should be recruited.

Study procedures

This phase of the study starts in November 2017.

General Practitioners (GPs) sampling is made according to existing files of previous projects adherent GPs, in other epidemiological studies. After the selection of GPs, those who accept to participate will recruit their own patients. Assuming that a GP will be able to include at least 6 patients in a 3-week period, a total of 65 GPs will be enrolled in the study: 21 in North of Portugal (31.7%), 16 in Centre of Portugal (24.7%), 18 in Lisbon-Tejo Valley (27.4%), 5 in Alentejo (8.4%), 3 in Algarve (4.3%), 1 in Azores (1.6%) and 1 in Madeira (1.9%) in accordance with the distribution of Portuguese old adult population (≥ 65 years) in Portugal according with Pordata (www.pordata.pt).

Enrolled GPs will be instructed to collect all necessary data about all older adults (≥ 65 years) patients attending a primary care consultation during the period of study: 5 days on 3 consecutive weeks (Monday and Tuesday on week 1; Wednesday and Thursday on week 2; and Friday on week 3).

Data collection

The collection of the data will occur in November 2017.

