GPs will be responsible for collecting all data about patients' sociodemographic characteristics, as well as morbidity and medication, during their consultations.

Data will be electronically stored in a database specifically designed for this study using MS Access 2010. Data will be encrypted and password protected. Information will be treated in strict confidentiality to protect the privacy of patients. The investigators will have no access to the data of the patient, except the one provided by the GP meaning that the only person to know who is being studied is the GP.

Before the collection of data, there will be online reunions with the GPs participating in the study.

Phase II: patients' perception of barriers to and facilitators of deprescribing, willingness to be deprescribed and actual self-medication in adult patients with polypharmacy attending primary care in Portugal

Objectives

To assert reasons and facilitators, willingness to be deprescribed and actual self-medication

Design

Cross-sectional, analytical study.

Setting

It will be the same of the phase I.

Sample size

A minimum of 385 patients will be included in phase II in order to obtain a sample with a 95% CI and a maximum precision error of 5%.

Study procedures

This phase of the study is expected to start in June 2018.

Again, GPs sampling will be made according to existing files and those who accept to participate will recruit their own patients. Patients from phase I can be enrolled in phase II. Assuming that a GP will be able to include at least 6 patients in a 3-week period, a total of 65 GPs has to be enrolled in the study, with the same distribution of the phase I. Enrolled GPs will be instructed to invite all older adult (≥ 65 years) patients attending the primary care consultation to participate in the study during 5 days on 3 consecutive weeks (Monday and Tuesday on week 1; Wednesday and Thursday on week 2; and Friday on week 3). Those willing to participate in the study must give written informed consent and present willingness and ability to comply with the study requirements.

Exclusion criteria will be: Being acutely unwell in the last three weeks, and refuse to participate.

Data collection

The collection of the data will occur in June 2018.

Patient's socio-demographic and clinical characteristics and medication will be registered using the same methodology as described in phase I.

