Perception of medication will be evaluated using Portuguese general BMQ, the willingness to be deprescribed will be assessed with two open-questions (one to assess the facilitators and the other to assess the barriers), and the actual self-medication will be evaluated with an analogic visual scale (0 to 10) about the need to self-medicate and its justification.

For those not knowing how to write or read, someone of their knowledge, will fill in the open questions, with their answers.

In case of less than 5% of answers of the open questions, two patient groups will be invited to make a focus group asserting reasons for accepting deprescribing.

Phase III: impact of enablement of older adults in their willingness to deprescribe and quality of life

Design

Non-pharmacological randomised clinical study, intended to last for six months.

Setting

Primary Care Centres in Portugal will be randomly selected from six Health Centres of Centre of Portugal (Aveiro, Castelo Branco, Coimbra, Guarda, Leiria and Viseu)

Sample size

Will be created two groups with a minimum of 190 patients each (one will be the intervention group and the other the control).

Study procedures

This phase of the study is expected to start in September 2019 and will last for 6 months.

Again, GPs sampling will be made according to existing files and those who accept to participate will recruit their own patients. Patients from previous phases can be enrolled in phase III. Assuming that a GP will be able to include at least 6 patients, a total of 64 GPs has to be enrolled in the study. Enrolled GPs will be instructed to invite all older adult (≥ 65 years) patients attending to the primary care consultation to participate in the study during until obtaining the sample size and being randomized according to the table for study entry. The geographical areas of work, the Districts, will be randomized for entry into exposed and unexposed groups. Those patients willing to participate in the study must give written informed consent and present willingness and ability to comply with the study requirements.

Exclusion criteria: Being acutely unwell in the last three weeks, and refuse to participate.

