Two groups will be created with a minimum of 190 patients each, one of which will be composed from patients from the region of Aveiro, Coimbra and Guarda and the other from patients from the region of Castelo Branco, Leiria and Viseu. In the intervention group we will give enablement tools and talks with their GPs about how to issue the problem of polypharmacy. The information given in this group will result from the knowledge obtained in phase II in the shape of small leaflets and other information materials to be made according to the best practice, to be given and remembered at scheduled times to the intervention group.

Data collection

The collection of the data will occur in the beginning and end of phase II.

Patient's socio-demographic and clinical characteristics and medication will be registered using the same methodology as described in phase I.

Perception of medication will be evaluated using Portuguese general BMQ, the willingness to be deprescribed will be assessed with two open-questions (the same as phase II), and the quality of life we will assessed with EQ-5D.

For those not knowing how to write, someone of their knowledge, will fill in the open questions.

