8 STATISTICAL CONSIDERATIONS

8.1 STATISTICAL HYPOTHESES

The investigators' hypothesis is that the intervention will result in statistical higher willingness to be deprescribed and better quality of life.

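### The only instrument assigned to the primary outcome, willingness to be deprescribed, is two open questions on facilitators and barriers; the protocol does not show that they yield a level of willingness or a yes/no answer.

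*Protocol*

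**What the plan says.** Protocol section 3 states the aim: "Primary objective is to assess the enablement of older adults while being Deprescribed in the rise of Willingness to be Deprescribed". Section 8.1 makes it a directional expectation, that "the intervention will result in statistical higher willingness to be deprescribed and better quality of life".

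Three places name a measure of willingness:

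- Section 4, Phase II data collection: "the willingness to be deprescribed will be assessed with two open-questions (one to assess the facilitators and the other to assess the barriers".
- Section 4, Phase III data collection: "the willingness to be deprescribed will be assessed with two open-questions (the same as phase II".
- Section 7.1: "Two open-questions (one to assess the facilitators and the other to assess the barriers", with the assessment of willingness given as their purpose.

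Section 7.1 assigns the BMQ to perception of medication and the EQ-5D to quality of life. The only rating scale in the protocol, a 0 to 10 visual analogue scale in Phase II, is assigned to self-medication. The text of the two open questions is not printed anywhere.

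**The concern.** A rise in willingness, or higher willingness in one group, can be tested only if each patient supplies something that can be ordered or classified: a grade, a score, or a yes or no. A question about what would help and a question about what stands in the way produce lists of reasons. If that is all that is asked, the primary hypothesis would be tested on a variable coded from reasons, and its link to willingness is not established in the protocol.

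The loss could not be repaired later. A statistical analysis plan can lay down how free text is coded, but it cannot supply an answer that patients were never asked to give.

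**Working it through.** The point rests on reading the sections together, not on a calculation.

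**1. What the objective needs.** Sections 3 and 8.1 both require a quantity that can be larger in the intervention group than in the control group.

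**2. What is collected for it.** Both data-collection paragraphs in section 4 and section 7.1 agree: two open questions and nothing else. The BMQ, the EQ-5D and the self-medication scale are each tied to another construct. No closed item, rating or score for willingness appears in the protocol.

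**3. Whether another section fills the gap.** Section 8.3 lists tests for qualitative and quantitative variables in general and names no willingness variable. Section 8.2 bases the sample size on a 95% confidence interval and 5% precision. With an assumed proportion of 0.5, which the protocol does not state, the usual formula is n = 1.96² × 0.5 × 0.5 / 0.05² = 384.1, rounded up to 385. This equals the Phase I and II figure and is close to the 380 given for Phase III. It is the precision of one proportion, and the protocol does not say of what. So section 8.2 does not define the willingness measure either.

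**4. Whether reasons can stand in for willingness.** As an illustration, take one patient who would accept stopping a medicine and one who would refuse. Both may name their doctor's advice as a facilitator and fear of returning symptoms as a barrier. Their coded answers are the same and their willingness is opposite. The Introduction (section 2) makes a related point: older people may dislike taking many medicines and still be reluctant to stop some.

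**5. What error would follow.** Suppose the free text is coded as willing or not willing, with sensitivity Se and specificity Sp against true willingness p. The proportion coded willing is Se × p + (1 − Sp) × (1 − p).

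- If Se and Sp are the same in both groups, the observed difference is (Se + Sp − 1) times the true one. With imperfect coding that is better than chance, this is a dilution.
- If they differ between groups (1 = intervention, 0 = control) and true willingness is the same p in both, the observed difference is (Se₁ − Se₀) × p + (Sp₀ − Sp₁) × (1 − p). This is generally not zero and can have either sign.

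The second case is plausible here. Section 4 says that the Phase III intervention materials come from the knowledge gained in Phase II, the phase that asks about barriers and facilitators. Intervention patients could repeat leaflet content in their answers without being more willing. No accuracy figure for any coding is in the documents, so no numbers can be put in.

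**The case against.** The strongest objection is that the wording of the questions is not shown. Section 7.1 says they serve to assess willingness. The Phase II fallback focus group concerns reasons for accepting deprescribing, which suggests that acceptance was in the investigators' minds. The questions may therefore include an acceptance answer, and the analysis plan, which is not at hand, may say how to code it. This stands to the extent that a reader should not infer that willingness is certainly not measured. The documents do not settle that. What remains is that the protocol fixes the primary instrument, describes it as asking about facilitators and barriers, and does not show that it returns the quantity the objective needs.

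A reader may also point out that the protocol lists barriers and facilitators apart from willingness: the synopsis ("assess the barriers and facilitators of deprescribing perceived by older adults, as well as their willingness to be deprescribed"), the outline of Phase II in section 4 ("perception of Barriers to and Facilitators of Deprescribing, Willingness to be Deprescribed and Willingness to Self-medicate") and the Phase II objectives ("To assert reasons and facilitators, willingness to be deprescribed and actual self-medication"). This is only modest support. All three describe the cross-sectional phases, and the last names reasons and facilitators but not barriers.

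It is also tempting to infer that a real effect would be diluted by a stated fraction. That would need assumed accuracy values and equal error in both groups. The documents give no such values, and the origin of the leaflets makes equal error doubtful.

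**Conclusion.** The point holds as a mismatch between the primary objective and the instrument described for it. As written, the protocol would give no direct answer on its primary outcome, unless the unprinted questions contain one. The consequence is error of unknown size. It dilutes the difference if it is equal in the two groups, and biases it in either direction if it is not. No magnitude can be given from the documents. The conclusion assumes that the descriptions in sections 4 and 7.1 convey what the questions ask. What a trial allocated by district can detect is a separate matter and is not part of this point.

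**What to change.** In section 7.1 and in the Phase III data-collection paragraph of section 4:

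- Add one direct closed item on willingness to have a medicine stopped, graded or yes/no. Alternatively, use an existing deprescribing-attitudes questionnaire such as the one in reference 15, if a suitable Portuguese version is available; the protocol does not say whether one is.
- If the existing questions already ask about acceptance, print their wording and record that answer in closed form instead.
- Ask it of every Phase III participant at the beginning and end of Phase III. The present paragraph places the collection at the start and close of Phase II, which should be corrected.
- Name this measure as the primary endpoint and keep the two open questions as descriptive information.

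The cost is one extra item (or a longer questionnaire) at two time points and an amendment to two sections. The downsides are that the new measure has no Phase II counterpart and that a newly written single item has no validation behind it.

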7.2 ADVERSE EVENTS AND SERIOUS ADVERSE EVENTS

No adverse events are expected to occur.

8 STATISTICAL CONSIDERATIONS

8.1 STATISTICAL HYPOTHESES

The investigators' hypothesis is that the intervention will result in statistical higher willingness to be deprescribed and better quality of life.

8.2 SAMPLE SIZE DETERMINATION

According to the older adults population in the Centre of Portugal and with a 95% confidence interval and a maximum precision error of 5%, so a minimum of 380 patients should be recruited.

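### The Phase III sample size rests on a one-sample 5% precision criterion that does not hold for the 190 v 190 comparison the hypothesis needs

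*Protocol*

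**What the plan says.** Section 8.2 gives one reason for the Phase III size. Based on the older population of the Centre of Portugal, the calculation is made "with a 95% confidence interval and a maximum precision error of 5%, so a minimum of 380 patients should be recruited". Section 4 (Phase III, Sample size) divides that total: "Will be created two groups with a minimum of 190 patients each (one will be the intervention group and the other the control".

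The hypothesis in section 8.1 compares the groups: "the intervention will result in statistical higher willingness to be deprescribed and better quality of life". Section 8.3 plans two-sided tests at 0.05.

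The same criterion sizes the cross-sectional Phase I survey in section 4: "we used a 95% confidence interval (CI) and a maximum precision error of 5%, so a minimum of 385 patients should be recruited". Phase II uses it as well.

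On allocation, section 4 (Phase III, Study procedures) speaks of patients "being randomized according to the table for study entry" and then says "The geographical areas of work, the Districts, will be randomized for entry into exposed and unexposed groups". It goes on to form the two groups from three named districts each, "one of which will be composed from patients from the region of Aveiro, Coimbra and Guarda". On the endpoint, "the willingness to be deprescribed will be assessed with two open-questions (the same as phase II"; the protocol fixes no scale for the answers.

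**The concern.** A margin of 5 points with 95% confidence describes how well a single proportion is estimated in a single sample. That suits Phases I and II. Phase III asks whether willingness is higher with the intervention than without it, so the quantity that matters is a difference between two groups of half the size. Its interval is wider for two reasons: each group has 190 patients rather than 380, and the errors of both groups add. If whole districts are allocated, patients in the same district are also not independent, and only six units carry the comparison.

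A reader of section 8.2 would expect 5-point precision, which the comparison does not have. The section gives no target difference and no power, so a null result could not be interpreted against it.

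**Working it through.** **Inputs from the protocol:** total 380 and a 5-point margin at 95% (section 8.2); 190 per group (section 4); two-sided 0.05 (section 8.3); six districts, three per group (section 4).

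**Assumptions, not in the protocol:** p = 0.5, the usual worst case for a maximum margin of error, with p = 0.8 as a second case; a binary endpoint, with a quantitative endpoint as the alternative; a district intraclass correlation (ICC) of 0.001, 0.01 or 0.05; equal numbers per district.

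**1. The plan's own figure.** n = 1.96² × 0.25 / 0.05² = 384.1, which rounds up to the 385 of Phase I. A finite-population correction lowers it slightly; exactly 380 would need a population of about 28,300 to 35,100, and the protocol gives no population size. With n = 380 the half-width is 1.96 × √(0.25/380) = 5.03 points. So 380 is consistent with a one-sample calculation at p = 0.5.

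**2. The same criterion applied to the groups, independent patients.**
- One group, p = 0.5: 1.96 × √(0.25/190) = ±7.1 points.
- Difference, p = 0.5: 1.96 × √(2 × 0.25/190) = ±10.05 points.
- Difference, p = 0.8: 1.96 × √(2 × 0.16/190) = ±8.0 points.

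The interval for the difference is thus 8.0/5 = 1.6 to 10.05/5 = 2.0 times as wide as the stated 5 points.

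**3. Power, 190 v 190, two-sided 0.05, independent patients** (normal approximation, pooled variance under the null).

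| Control v intervention | Power |
|---|---|
| 50% v 55% | 16% |
| 50% v 60% | 50% |
| 50% v 64.2% | 80% |
| 80% v 90.2% | 80% |

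**4. Quantitative endpoint, unadjusted, independent patients.** Half-width 1.96 × √(2/190) = ±0.20 SD. Difference detectable with 80% power: (1.96 + 0.84) × √(2/190) = 0.29 SD.

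**5. Districts as the unit, three v three.** Patients per district m = 190/3 = 63.3. Design effect DE = 1 + (63.3 − 1) × ICC. With six districts in two groups, 6 − 2 = 4 degrees of freedom remain, and t(0.975, 4) = 2.776. At p = 0.5 the standard error (SE) of the difference is √(0.5 × DE/190), and the half-width is 2.776 × SE. Power of 80% needs a difference of 3.76 SE (noncentral t, 4 df, variance held at its p = 0.5 value). In SD units the SE is √(2 × DE/190).

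| Assumed ICC | DE | Half-width, points | 80% power at, points | Half-width, SD |
|---|---|---|---|---|
| 0.001 | 1.06 | ±14.7 | 19.9 | ±0.29 |
| 0.01 | 1.62 | ±18.1 | 24.6 | ±0.36 |
| 0.05 | 4.12 | ±28.9 | 39.1 | ±0.58 |

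These half-widths are 14.7/5 = 2.9 to 28.9/5 = 5.8 times the stated 5 points. Using the normal quantile instead of t would give ±12.8 and ±20.4 points at ICC 0.01 and 0.05, still far above 5.

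**The case against.** - **380 is correct arithmetic, and the trial may be adequately powered.** Both parts are fair. The figure is sound for one sample, and with independent patients 190 v 190 has 80% power at about 14 points from 50%. The fault is the mismatch between criterion and hypothesis, not an error of calculation or proven underpowering.
- **Sample-size detail may sit in an unseen SAP.** The protocol did not leave it there. It has a sample-size section, fixes the total in it and gives a reason that does not fit the design. How the open questions are coded could be left to the SAP, but a size calculation cannot be stated without naming the scale it assumes.
- **Five points can hold for some proportions.** It holds per group from p of about 0.86, and for the difference from about 0.93 (or at the mirror values near zero). But the plan claims a maximum error, which means the worst case, and gives no expected willingness that would justify such extremes.
- **The district figures depend on an assumed ICC and a t on 4 df that section 8.3 does not name.** This is true, and they are illustrative. The direction does not depend on them: even independence gives more than 5 points.
- **The reference to a table for study entry may concern enrolment, not allocation to a group.** That reading is possible, and the district reading has the stronger textual support. The sentence still calls patients randomised immediately before it calls districts randomised, so the unit needs stating once.
- **Baseline data and ANCOVA could sharpen the comparison.** They could. The figures above are unadjusted, and the protocol gives no correlation from which to compute a gain.
- **Stating a detectable difference for a fixed size does not justify that size.** This stands. It makes the sensitivity visible, so that the sponsor can judge whether 190 per group suffices.

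**Conclusion.** The concern holds and must be fixed. The one precision figure in section 8.2 describes a proportion pooled over both groups, which is not what section 8.1 tests. For a binary endpoint and independent patients, the between-group interval is 1.6 to 2 times as wide as stated (p = 0.8 to 0.5). With three districts per group it is about 3 to 6 times as wide at p = 0.5, over an assumed ICC of 0.001 to 0.05. The mismatch itself needs no assumption beyond reading the stated margin as a worst case. The sizes depend on the endpoint scale, the control value and the ICC, none of which the protocol gives.

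**What to change.** Keep 190 per group and make four changes.

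1. In section 4 (Phase III, Study procedures), state one unit of randomisation, patients or districts, and remove the conflicting wording.
2. In section 8.2, delete the 5% precision statement as the justification for Phase III.
3. In its place, state the scale of the primary willingness endpoint, the assumed control value or SD, and the 95% CI half-width and 80%-power detectable difference for 190 v 190. For independent patients, examples are ±10.05 and 14.2 points (binary, control 50%), ±8.0 and 10.2 points (binary, control 80%), or ±0.20 SD and 0.29 SD (quantitative, before any gain from baseline adjustment).
4. If districts are the unit, do not use the independence figures. Give them inflated for three districts per group over a stated ICC range, for example 0.001 to 0.05 with t on 4 df.

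The cost is new wording in section 8.2 and one reconciliation in section 4. No patients are added; the stated precision becomes less favourable.
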